7.7.3 Laboratory Evaluations

Safety laboratory tests of chemistry, hematology/coagulation, and endogenous FGF21 ([Table 5](#)) received from central laboratory will be summarized (n, mean, SD, median, minimum, and maximum) by treatment group and study visit along with the corresponding change from baseline values. Data for all laboratory tests, including urine/miscellaneous, unscheduled local laboratory tests recorded to the eCRF, and any additional analytes will be listed.

CONFIDENTIAL

Document Date: 07 Feb 2024

Page 46 of 60
ST-AD-008 version 05

Statistical Analysis Plan

Sponsor Name: Akero Therapeutics, Inc.
 Sponsor Protocol ID: AK-US-001-0102

Table 5 Clinical Laboratory Assessments

Chemistry	Hematology/ Coagulation	Urine/ Miscellaneous	
Sodium Potassium Chloride Bicarbonate Calcium Magnesium Phosphorus Glucose ^b BUN Creatinine Total protein Albumin Uric acid LDH	Total bilirubin (TBL) direct bilirubin Alkaline phosphatase (ALP) ALT (SGPT) AST (SGOT) GGT CK hsCRP Amylase Lipase ^c 3 Hydroxybutyrate	Hematology RBC count Hemoglobin (Hgb) Hematocrit (Hct) Platelet count WBC count with differential: neutrophils, lymphocytes, monocytes, eosinophils, and basophils ANC Coagulation PT aPTT INR PAI-1 Fibrinogen	Urine Drug screening: amphetamines, cocaine and opiates (i.e., heroin, morphine) Miscellaneous Screening Serology Tests HBsAg HBcAb HBV DNA Hep A IgM Anti-HCV antibody HCV RNA HIV Endogenous FGF21 ^b Pregnancy test ^a

ALT = alanine aminotransferase; ANC = absolute neutrophil count; AST = aspartate aminotransferase; aPTT = activated partial thromboplastin time; BUN = blood urea nitrogen; GGT = gamma-glutamyl transferase; HbA1c = Glycated Hemoglobin A1c; HBcAb = total hepatitis B core antibody; HBsAg = hepatitis B surface antigen; HBV DNA = hepatitis B virus deoxyribonucleic acid; HCV = hepatitis C virus; HIV = human immunodeficiency virus; hsCRP = high sensitivity C-Reactive Protein; INR = International Normalized Ratio; LDH = lactate dehydrogenase; PAI-1 = Plasminogen Activator Inhibitor-1; PT = prothrombin time; RBC = red blood cell; RNA = ribonucleic acid; TBL= total bilirubin; WBC = white blood cell

^a For female subjects of childbearing potential only. Serum pregnancy test at screening and urine pregnancy test at other time points.

^b Samples to be collected in the morning following an overnight fast of at least 8 hours.

^c Reflex lipase testing is performed in subjects with total amylase > 1.5 ULN.

All laboratory data will be reported in Conventional units. Out-of-reference-range values will be flagged as high (H) or low (L) in the listings. For analysis purposes, values preceded by a "<" or a ">" sign (i.e. those below or above the limits of quantification) will be considered equal to the lower or upper limit of quantification, respectively.

Baseline for each laboratory analyte is the pre-dose measurement on Baseline visit (Day 1) with exceptions as defined in Section 7.1.1. For post-baseline, within an analysis visit window, the analyte measurement from the scheduled visit will be used if available. If multiple scheduled visits occur within a single visit window, then the visit closest to the target day of the visit window will be used in the analysis. If there is a tie, the later visit will be used in the analysis.

Statistical Analysis Plan

Sponsor Name: Akero Therapeutics, Inc.
Sponsor Protocol ID: AK-US-001-0102

If no scheduled visit occurs, the measurement from the unscheduled visit closest to the defined target analysis day within the window will be used. If there is more than one measurement with equal distance to the defined target analysis day, the latter will be used. If no visits occur within a visit window, the measurement for this visit will be treated as missing.

Laboratory values will be assigned toxicity grades, when available, using criteria based on the NCI-CTCAE, version 5.0 (Table 6). These criteria are derived using only the numeric laboratory measurement, baseline measurement and normal range limits. Where defined, low and high shifts will be summarized separately. The incidence of treatment-emergent laboratory abnormalities, defined as values that increase at least one toxicity grade from baseline at any scheduled or unscheduled post-baseline assessment up to and including the date of last dose of study drugs plus 30 days, will be summarized by treatment group and visit. If baseline data are missing, then any graded abnormality (i.e., at least a Grade 1) will be considered treatment-emergent. The percentage incidence of graded treatment-emergent abnormalities will be calculated out of the number of subjects with non-missing value at the specified time point.

Table 6 Laboratory Toxicity Grade Criteria of Selected Clinical Laboratory Assessments

Serum Chemistry	CTCAE Term	Grade 1	Grade 2	Grade 3	Grade 4
ALT	Alanine aminotransferase increased	>ULN - 3.0 x ULN if baseline was normal; 1.5 - 3.0 x baseline if baseline was abnormal	>3.0 - 5.0 x ULN if baseline was normal; >3.0 - 5.0 x baseline if baseline was abnormal	>5.0 - 20.0 x ULN if baseline was normal; >5.0 - 20.0 x baseline if baseline was abnormal	>20.0 x ULN if baseline was normal; >20.0 x baseline if baseline was abnormal
AST	Aspartate aminotransferase increased	>ULN - 3.0 x ULN if baseline was normal; 1.5 - 3.0 x baseline if baseline was abnormal	>3.0 - 5.0 x ULN if baseline was normal; >3.0 - 5.0 x baseline if baseline was abnormal	>5.0 - 20.0 x ULN if baseline was normal; >5.0 - 20.0 x baseline if baseline was abnormal	>20.0 x ULN if baseline was normal; >20.0 x baseline if baseline was abnormal
TBILI	Blood bilirubin increased	>ULN - 1.5 x ULN if baseline was normal; >1.0 - 1.5 x baseline if baseline was abnormal	>1.5 - 3.0 x ULN if baseline was normal; >1.5 - 3.0 x baseline if baseline was abnormal	>3.0 - 10.0 x ULN if baseline was normal; >3.0 - 10.0 x baseline if baseline was abnormal	>10.0 x ULN if baseline was normal; >10.0 x baseline if baseline was abnormal
ALP	Alkaline phosphatase increased	>ULN - 2.5 x ULN if baseline was normal; 2.0 - 2.5 x baseline if baseline was Abnormal	>2.5 - 5.0 x ULN if baseline was normal; >2.5 - 5.0 x baseline if baseline was Abnormal	>5.0 - 20.0 x ULN if baseline was normal; >5.0 - 20.0 x baseline if baseline was abnormal	>20.0 x ULN if baseline was normal; >20.0 x baseline if baseline was abnormal

CONFIDENTIAL

Statistical Analysis Plan

Sponsor Name: Akero Therapeutics, Inc.
 Sponsor Protocol ID: AK-US-001-0102

Serum Chemistry	CTCAE Term	Grade 1	Grade 2	Grade 3	Grade 4
Creatinine (Cr)	Creatinine increased	>ULN - 1.5 x ULN	>1.5 - 3.0 x baseline; >1.5 - 3.0 x ULN	>3.0 x baseline; >3.0 - 6.0 x ULN	>6.0 x ULN
CPK	CPK increased	>ULN - 2.5 x ULN	>2.5 - 5.0 x ULN	>5 - 10 x ULN	>10 x ULN
Potassium (K)	Hyperkalemia	>ULN - 5.5 mmol/L	>5.5 - 6.0 mmol/L	>6.0 - 7.0 mmol/L	>7.0 mmol/L
Amylase	Serum amylase increased	>ULN - 1.5 x ULN	>1.5 - 2.0 x ULN; >2.0 - 5.0 x ULN and NCS	>2.0 - 5.0 x ULN and CS; >5.0 x ULN and NCS	>5.0 x ULN and CS
Glucose	Hypoglycemia	<LLN - 55 mg/dL; <LLN - 3.0 mmol/L	<55 - 40 mg/dL; <3.0 - 2.2 mmol/L	<40 - 30 mg/dL; <2.2 - 1.7 mmol/L	<30 mg/dL; <1.7 mmol/L
GGT	GGT increased	>ULN - 2.5 x ULN if baseline was normal; >2 - 2.5 x baseline if baseline was abnormal	>2.5 - 5.0 x ULN if baseline was normal; >2.5 - 5.0 x baseline if baseline was abnormal	>5.0 - 20.0 x ULN if baseline was normal; >5.0 - 20.0 x baseline if baseline was abnormal	>20.0 x ULN if baseline was normal; >20.0 x baseline if baseline was abnormal

Hematology	CTCAE Term	Grade 1	Grade 2	Grade 3	Grade 4
Hemoglobin	Anemia	<LLN - 10.0 g/dL; <LLN - 6.2 mmol/L; <LLN - 100 g/L	<10.0-8.0 g/dL; <6.2 - 4.9 mmol/L; <100 - 80g/L	<8.0 g/dL; <4.9 mmol/L; <80 g/L	
Hemoglobin	Hemoglobin increased	>ULN & increase in >0 - 2 g/dL	>ULN & increase in >2 - 4 g/dL	>ULN & increase in >4 g/dL	
CD4 lymphocytes	CD4 lymphocytes decreased	<LLN - 500/mm ³ ; <LLN - 0.5 x 10e9/L	<500 - 200/mm ³ ; <0.5 - 0.2 x 10e9/L	<200 - 50/mm ³ ; <0.2 - 0.05 x 10e9/L	<50/mm ³ ; <0.05 x 10e9/L
Neutrophils	Neutrophil count decreased	<LLN - 1500/mm ³ ; <LLN - 1.5 x 10e9 /L	<1500 - 1000/mm ³ ; <1.5 - 1.0 x 10e9 /L	<1000 - 500/mm ³ ; <1.0 - 0.5 x 10e9 /L	<500/mm ³ ; <0.5 x 10e9 /L
White Blood Cell (WBC) Count	White blood cell decreased	<LLN - 3000/mm ³ ; <LLN - 3.0 x 10e9 /L	<3000 - 2000/mm ³ ; <3.0 - 2.0 x 10e9 /L	<2000 - 1000/mm ³ ; <2.0 - 1.0 x 10e9 /L	<1000/mm ³ ; <1.0 x 10e9 /L
Platelet Count	Platelet count decreased	<LLN - 75000/mm ³ ; <LLN - 75.0 x 10e9 /L	<75000 - 50000/mm ³ ; <75.0 - 50.0 x 10e9 /L	<50000 - 25000/mm ³ ; <50.0 - 25.0 x 10e9 /L	<25000/mm ³ ; <25.0 x 10e9/L

Coagulation	CTCAE Term	Grade 1	Grade 2	Grade 3	Grade 4
INR	INR increased	>1.2 - 1.5; >1 - 1.5 x baseline if on anticoagulation	>1.5 - 2.5; >1.5 - 2.5 x baseline if on anticoagulation	>2.5; >2.5 x baseline if on anticoagulation	

For other parameters, not listed in [Table 6](#) separate laboratory shift tables will present directional shifts from baseline to above the laboratory standard upper limit

CONFIDENTIAL

Statistical Analysis Plan

Sponsor Name: Akero Therapeutics, Inc.
Sponsor Protocol ID: AK-US-001-0102

of normal (ULN) or below the lower limit of normal (LLN) using the maximum increase and/or decrease observed throughout the course of treatment and including the 30-day follow-up visit. Scheduled and unscheduled assessments will be included in this analysis.

Evaluation of drug-induced serious hepatotoxicity (eDISH) plot will be provided to display peak serum ALT and total bilirubin (TB) levels for each subject. The peak serum AST versus TB levels for each subject will also be provided.

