1.3. Nonclinical Pharmacology & Toxicology

In vitro characterization of EFX demonstrated high affinity binding (<10nM) to human, cynomolgus monkey, and mouse β -Klotho. EFX was demonstrated to activate c-isoforms of FGFR: FGFR1c, 2c and 3c, with balanced potency and high selectivity over FGFR4 using a cell-line co-expressing human β -Klotho and each FGFR individually (Stanislaus et al. 2017).

In vivo, EFX is pharmacologically active in rodents and monkeys. Administration of EFX to obese and insulin resistant mouse and monkey models improved the metabolic status of these animals resulting in reduced plasma glucose, insulin, and triglyceride levels; improved lipoprotein profile; enhanced glucose tolerance; and significant weight loss (Stanislaus et al. 2017).

EFX has been evaluated in 16- and 26-week nonclinical toxicology studies in rats and monkeys administered subcutaneous doses of 0 (vehicle control), 10, 30, or 100 mg/kg once weekly. Effects observed in these studies in both species included decreases in body weight gain/body weight, decreases in lean body mass and body fat, decreased bone growth secondary to effects on body weight, and minimal increases in ALT and or AST without concomitant liver pathology. Increased adipocyte cellularity in bone marrow was observed in rats. These effects were consistent with and attributed to the known pharmacological effects of FGF21 analogs such as EFX. Decreased red cell mass (erythrocytes, hemoglobin, and/or hematocrit), decreased thymic lymphoid cellularity, decreases in reproductive organ weights in both sexes, and minimal to mild atrophy of uterus, cervix, and vagina in monkeys were attributed to stress and/or reduced body weight/growth. EFX-related changes were

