6.13. Clinical Laboratory Tests

6.13.1. Laboratory Parameters

Blood samples will be collected according to the Schedule of Assessments ([Appendix A - B](#)) and below. Samples will be sent to the central laboratory for analysis and reporting. Samples may be analyzed for the tests outlined in this protocol and for any additional tests necessary to ensure subject safety. These may include, but are not limited to, investigation of unexpected results and incurred sample reanalysis.

At visits where indicated, samples should be collected in the morning following an overnight fast of at least 8 or 12 hours.

Subjects will be in a seated, semi-recumbent, or supine position during blood collection. Clinical laboratory tests will include the following:

Table 5. Clinical Laboratory Assessments

Chemistry	Hematology/Coagulation	Urine/Miscellaneous	Biomarkers
Sodium	Hematology	Urine	Fibrosis Biomarkers
Potassium	RBC count	Drug screening: amphetamines, cocaine and opiates (i.e., heroin, morphine)	ELF
Chloride	Hemoglobin (Hgb)		Pro-C3
Bicarbonate	Hematocrit (Hct)		C3M
Calcium	Platelet count		NIS-4 ^d
Magnesium			
Phosphorus	WBC count with differential: neutrophils, lymphocytes, monocytes, eosinophils, and basophils	Miscellaneous	Bone Biomarkers
Glucose ^b		Screening Serology Tests	P1NP
BUN			CTX-1 ^b
Creatinine			
Total protein		HBsAg	Lipid Metabolism Biomarkers
Albumin	ANC	HBcAb	ApoB & ApoC3
Uric acid		HBV DNA	
LDH	Coagulation	Hep A IgM	
Total (TBL) and direct bilirubin	PT	Anti-HCV antibody	Insulin Sensitivity & Glycemic Control Biomarkers
Alkaline phosphatase (ALP)	aPTT	HCV RNA	Insulin
ALT (SGPT)	INR	HIV	Adiponectin
AST (SGOT)	PAI-1		C-Peptide
GGT	Fibrinogen	Endogenous FGF21 ^b	HOMA-IR ^b
CK			
hsCRP		Pregnancy test ^a	
Amylase			
Lipase ^c		Pharmacokinetics (PK)	
3 Hydroxybutyrate			
HbA1c			
Lipoproteins			
Lp (a)		Anti EFX antibody (ADA)	
NMR LipoProfile ^b (includes Total Cholesterol, HDL-C, LDL-C, LDL-P, Triglycerides)		Neutralizing Anti EFX antibody (NAB)	

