7.8.3. Laboratory Evaluations

Selected laboratory data will be summarized (n, mean, SD, median, minimum, and maximum) by treatment group and study visit along with the corresponding change from baseline values.

Graded laboratory abnormalities will be defined using the grading scheme in the CTCAE. Grading of laboratory abnormalities for analysis purposes will be defined in the Statistical Analysis Plan.

The incidence of treatment-emergent laboratory abnormalities, defined as values that increase at least one toxicity grade from baseline at any time post baseline up to and including the date of last dose of study drugs plus 30 days, will be summarized by treatment group. If baseline data are missing, then any graded abnormality (i.e., at least a Grade 1) will be considered treatment-emergent.

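### SAP Table 6 grades CD4 lymphocytes, which no planned test measures, and gives no grade to the total lymphocyte count, which is measured throughout

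*SAP*

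**What the plan says.** Protocol 7.8.3 leaves the matter to the SAP: "Grading of laboratory abnormalities for analysis purposes will be defined in the Statistical Analysis Plan". SAP 7.7.3 then assigns grades from Table 6, using criteria based on NCI-CTCAE v5.0.

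The haematology block of Table 6 contains a row headed "CD4 lymphocytes decreased", with limits running from below the lower limit of normal (LLN) down to under 50/mm³ for Grade 4.

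The planned haematology tests are in Table 5 of the protocol (6.13.1) and Table 5 of the SAP (7.7.3). Both list "WBC count with differential: neutrophils, lymphocytes, monocytes, eosinophils, and basophils". Neither lists CD4 or any other lymphocyte subset.

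Two further rules in SAP 7.7.3 matter. The percentage with a graded treatment-emergent abnormality "will be calculated out of the number of subjects with non-missing value at the specified time point". For analytes without a row in Table 6, "separate laboratory shift tables will present directional shifts from baseline to above the laboratory standard upper limit" of normal (ULN) or below the LLN.

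**The concern.** A grading table should grade what the trial measures. Here one row refers to a test that is not planned, while the closest measured analyte has no row. The likely explanation is that the wrong CTCAE term was picked for lymphocytes, although the documents do not say so.

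Grade is how this plan expresses laboratory severity: SAP 7.7.3 and Protocol 7.8.3 both define a treatment-emergent laboratory abnormality as a rise of at least one toxicity grade from baseline. An analyte without grades cannot enter that incidence table. At stake is the graded, by-arm comparison of low lymphocyte counts, which the existing data could supply.

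**Working it through.** No figure in the plan needs to be reproduced. The check sets the tables side by side.

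**1. Does each graded haematology row have a planned test?**

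| Table 6 haematology row | Protocol Table 5 | SAP Table 5 |
|---|---|---|
| Hemoglobin, low | yes | yes |
| Hemoglobin, high | yes | yes |
| CD4 lymphocytes | **no** | **no** |
| Neutrophils | yes | yes |
| White cell count | yes | yes |
| Platelets | yes | yes |

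The 10 chemistry rows and the INR row also match planned tests. Table 6 therefore has 10 + 6 + 1 = 17 rows, of which 16 have a planned test and 1 does not.

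**2. What does the CD4 row produce?** The denominator is the number of subjects with a value at the time point. With no planned CD4 assay, that number is 0 at every scheduled visit, so the row is empty.

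**3. Is the total lymphocyte count graded anywhere else?** The protocol hands grading for analysis to the SAP, the SAP grades from Table 6, and Table 6 has no total lymphocyte row. The count falls under the rule for analytes not in Table 6, which gives shifts past LLN or ULN only. In that shift table, a value just under LLN and a very low value share one cell.

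The white-cell and neutrophil rows are only a partial substitute. The white-cell count is the sum of the cell types in the differential, so a fall in lymphocytes can be offset by other cells and leave both graded counts normal.

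**4. How much data is involved?**
- The haematology windows in SAP 6.1 are Weeks 1, 4, 8, 12, 16, 20 and 24 (7 visits), Weeks 28 to 56 every 4 weeks (8), and Weeks 64, 72, 80, 88 and 96 (5). The total is 7 + 8 + 5 = 20.
- Protocol Appendices A and B agree: 7 visits to Week 24 and 13 after it, 7 + 13 = 20.
- Planned subjects: 3 arms × 40 = 120 (Protocol 5.2.2).
- Upper limit on scheduled post-baseline lymphocyte results: 120 × 20 = 2,400.

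The 2,400 measures the data collected, not the size of an effect. It assumes full attendance, and values within the normal range would carry no low-count grade anyway. The documents give no expected frequency of low counts, so the number of grades lost cannot be estimated.

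**The case against.** The strongest reply is that leaving lymphocytes ungraded is permitted. Table 6 is titled as covering selected assessments, there is an explicit rule for the rest, and other measured analytes (sodium, calcium, magnesium, lipase and fibrinogen, for example) have no row either. This stands as a defence of not grading lymphocytes. It does not defend a row for a test that is not planned.

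Some stronger readings are tempting, and the documents do not support them:

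- *Lymphopenia severity goes unreported.* It does not. SAP 7.7.3 gives by-visit summaries that include the minimum, listings with high and low flags, and shift tables based on the largest decrease, with unscheduled tests included. Under Protocol 6.22 and 6.24, a low count that is clinically significant, needs intervention, or leads to interruption of study drug is recorded as an adverse event and graded by CTCAE. That last route depends on investigator judgement, so it does not replace systematic grading.
- *Total lymphocytes would be graded against CD4 limits.* Nothing in the SAP maps the differential to that row, and both its label and its CTCAE term say CD4. Read literally, the row is empty, not wrong.
- *CD4 can never be measured.* Protocol 6.13.1 allows additional safety tests in general terms, and SAP 7.7.3 would list any additional analytes. The accurate statement is that CD4 is not among the planned tests.
- *The animal data signal lymphopenia in humans.* Protocol 1.3 reports "decreased thymic lymphoid cellularity", but this is a finding in the thymus, not in circulating counts. The same passage attributes it to stress or reduced body weight or growth, and describes the changes as generally reversible or tending that way. Lymphopenia is not listed as an event of special interest.
- *The DMC triggers in Protocol 6.22.3 are disabled.* Table 6 governs grading for analysis. Severity during conduct is graded directly by CTCAE v5.0 (Protocol 6.22.1 and 6.24).

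**Conclusion.** Wrong as written, minor. One of the 17 rows in Table 6 grades an analyte that is not a planned test, and the lymphocyte count collected at 20 scheduled post-baseline visits has no grade in the laboratory tables. The effect is confined to the graded laboratory safety tables: one empty row, and one missing graded display for an analyte that is otherwise summarised, listed and shown in shift tables. No efficacy endpoint, sample size or error rate is involved.

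This rests on the two Table 5 lists being the complete set of planned tests, and on the programmers following Table 6 literally. If the sponsor chose not to grade lymphocytes, the omission is a permitted choice, but the CD4 row still has nothing to report.

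**What to change.** In SAP Table 6, replace the CD4 row with the CTCAE v5.0 term for a decreased total lymphocyte count, and state that it applies to the lymphocyte count from the white-cell differential. Take the cut-offs from CTCAE v5.0 itself, since neither document gives them. The limits printed in the CD4 row should not be carried over, because CD4 cells are only a subset of lymphocytes.

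If the sponsor prefers to leave lymphocytes ungraded, delete the CD4 row, so that Table 6 agrees with Table 5 and lymphocytes fall openly under the shift-table rule. Replacement is better, because it adds a graded safety result from data already collected.

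The cost is one table row, the matching programming, and a line in the SAP's document history. No new sampling or assay is needed, and no efficacy output changes.

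### SAP 7.7.3 assigns laboratory analytes to categorical tables by analyte rather than by direction, so no table counts by arm the subjects with low potassium, high glucose, or high white cells, neutrophils or platelets

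*SAP*

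**What the plan says.** SAP 7.7.3 (Laboratory Evaluations) plans two categorical summaries.

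- **Graded abnormalities.** Values receive a CTCAE grade under Table 6, and the incidence of treatment-emergent graded abnormalities is tabulated by arm and visit. On direction the SAP says "Where defined, low and high shifts will be summarized separately".
- **Shift tables.** The text after Table 6 reads "For other parameters, not listed in" Table 6, "separate laboratory shift tables will present directional shifts from baseline to above the laboratory standard upper limit" of normal, or below the lower limit.

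In Table 6 the only potassium row is "Hyperkalemia" and the only glucose row is "Hypoglycemia". White cells appear only as "White blood cell decreased" and neutrophils only as "Neutrophil count decreased". Platelets likewise have a row only for a fall. Hemoglobin has one row for each direction.

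Protocol 7.8.3 says "Graded laboratory abnormalities will be defined using the grading scheme in the CTCAE" and leaves the details of grading for analysis to the SAP.

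**The concern.** The two summaries look complementary: an analyte is either graded or shifted. They would be complementary only if each analyte in Table 6 were graded in every direction that matters. For five analytes it is not, and the rule that sends an analyte to Table 6 also takes it out of the shift tables. Sodium, calcium and magnesium, which are not in Table 6, do get both directions.

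What is at stake is a simple safety count: how many subjects in each arm went out of range in the ungraded direction. Potassium is the clearest case. Diarrhea is a predefined event of special interest (Protocol 6.23, SAP 3.5), and low potassium is a familiar laboratory accompaniment of diarrhea. That link is general clinical knowledge and does not come from the documents. For glucose, Protocol 5.3 (Table 4) has sites remind subjects on insulin or sulfonylureas about symptoms of both low and high glucose, yet only low values are graded.

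**Working it through.** No sample size, power or error rate is involved, and the plan gives no figure to reproduce. The check sets the Table 6 rows against the scope of the shift tables, and then asks whether another output supplies the count.

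**Step 1. Coverage by direction**

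| Analyte | Graded in Table 6 | In shift tables? | Direction with no per-arm count |
|---|---|---|---|
| Potassium | high | no (listed) | low |
| Glucose | low | no (listed) | high |
| White cells | low | no (listed) | high |
| Neutrophils | low | no (listed) | high |
| Platelets | low | no (listed) | high |
| Hemoglobin (contrast) | low and high | no (listed) | none |
| Sodium, calcium, magnesium (contrast) | not listed | yes, both ways | none |

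The result is five analytes with one uncounted direction each. Other Table 6 analytes are also graded in one direction only, but for many of them the missing side matters little (low ALT, for example). They are left out of the size of this point.

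**Step 2. Does another output supply the count?**

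- *By-visit summaries (SAP 7.7.3).* These give continuous statistics, including minimum and maximum. They can show that an extreme value occurred but not how many subjects were out of range. They also use the scheduled result whenever one exists in the window, so an unscheduled potassium drawn during an illness would usually not reach the minimum. Both categorical tables do take in unscheduled results, but neither looks at low potassium.
- *Listings (SAP 7.7.3).* Out-of-range values carry an H or L flag subject by subject. Nothing is counted by arm.
- *Adverse event tables (SAP 7.7.2).* A laboratory value enters if the investigator judges it clinically significant (Protocol 6.22). It also enters if it needs intervention, leads to interruption or discontinuation of study drug, or comes with signs or symptoms that meet the adverse event definition (Protocol 6.24). An untreated, symptom-free low potassium that is not judged significant does not enter.
- *Glycemic analyses.* SAP 7.6.2.6 models HbA1c, C-peptide, adiponectin and HOMA-IR. SAP 7.6.3.7 compares new-onset type 2 diabetes using HbA1c. Neither counts high glucose values.
- *Protocol 7.8.3.* It delegates the grading, so it adds no further table.

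None of these closes the gap.

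**The case against.** The case on the other side has several parts, and most of it limits the point without removing it.

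- *A reader might infer a breach of the protocol.* The documents do not support that. Protocol 7.8.3 defines a treatment-emergent laboratory abnormality by a rise in grade and hands the grading to the SAP. A direction that the SAP chooses not to grade lies outside that commitment.
- *A reader might infer that these values are lost or go unwatched.* They do not. They reach the summaries and listings above, and a treated low potassium must be recorded as an adverse event. Sites grade laboratory abnormalities on CTCAE (Protocol 6.22.1), Grade 3 and 4 abnormalities trigger toxicity management (Protocol 6.24), and clusters of related events can convene the DMC (Protocol 6.22.3). The gap concerns the tabulation of mostly mild, untreated values.
- *A reader might infer that Table 6 analytes are covered less well overall.* In the graded direction they are covered better, because they get severity by visit where other analytes get only a shift.
- *The glucose part is weaker.* Hypoglycemia is the event of special interest and is the graded direction. Glycemia is analysed elsewhere through HbA1c and HOMA-IR, and many high glucose values would reflect known diabetes. This lowers the priority of high glucose, but the count is still missing.
- *"Parameters" could be read as directions.* That reading would close the gap, but the text does not say it and the word most naturally means the analyte. The SAP refers to table shells, which are not among the documents, so the final set of outputs cannot be confirmed.

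**Conclusion.** The point stands as a minor gap in safety tabulation. Under the rule as written, five directions have no per-arm count: low potassium, high glucose, and high white cells, neutrophils and platelets. Low potassium is the one most worth closing.

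The conclusion rests on two assumptions: that "For other parameters, not listed in" Table 6 refers to analytes, and that the unseen table shells do not go beyond the SAP text. The number of subjects affected cannot be estimated, because the documents give no rate of low potassium or of the other four abnormalities. There is no breach of the protocol, no failure of safety monitoring during the trial, and no effect on the primary analysis.

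**What to change.** In SAP 7.7.3, replace the opening of the shift-table sentence ("For other parameters, not listed in" Table 6) with: *For parameters, and for directions of change, not graded in Table 6*. Potassium below the lower limit, and glucose, white cells, neutrophils and platelets above the upper limit, then get the same shift table as the unlisted analytes, with unscheduled results included.

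The wording also brings in ungraded sides of little interest, such as low ALT. If the sponsor prefers fewer pages, the sentence can name the five directions instead. A new low-potassium grade row is not needed: its cut-offs are not in the documents, and the shift table alone restores the count.

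The cost is one sentence, made by SAP revision or documented clarification, and a few more output pages from data already collected. It needs no protocol amendment and no extra samples. This is a cheap improvement.
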